## Purpose of the Study

The objective of the study is to elucidate the potential mechanisms responsible for the increased risk of CVD among patients with hypertension and comorbid insomnia. To address this issue, we propose to utilize a behavioral intervention to manipulate sleep quality in 150 adults with hypertension and comorbid insomnia, who will receive a 6-week Cognitive Behavioral Therapy for Insomnia (CBT-I) intervention, which has been shown to markedly improve sleep quality and promote consolidated sleep in approximately 60% of those treated. Blunted nighttime blood pressure dipping is one of several proposed mechanisms to be examined.

## Background & Significance

There is a growing body of evidence that insomnia is a CVD risk factor. In a meta-analysis of 17 observational cohort studies, with a combined sample size of 311,260 participants free of CVD at baseline, Li and colleagues found that insomnia was associated with a 41% increased risk of myocardial infarction (MI), coronary heart disease (CHD), stroke, or CVD mortality over a 1-year follow-up period. Similarly, in an analysis of 13 prospective cohort studies of adults with insomnia (N=122,501), but absent of documented CVD, Sofi and colleagues found a 45% increased risk of developing or dying from CVD over a follow-up period of 3 years or more. As the latter authors, concluded, "Insomnia is associated with an increased risk of developing and/or dying from cardiovascular disease. The evidence that low-quality sleepers are at higher risk of myocardial infarction and other cardiovascular disease is extremely important for primary and secondary prevention." Even in the absence of an insomnia disorder diagnosis, poor sleep quality has been linked to CVD risk. In a meta-analysis of 20,432 adults, aged 20-65 years without history of CVD followed for 10-15 years, Hoevenaar-Blom et al. reported that poor sleep quality was associated with a 22% higher risk of developing CVD and a 34% higher risk of CHD incidence than those with good sleep quality. Lo and colleagues also recently reported a meta-analysis of studies including over 45,000 participants, spanning over 5 continents, showing that poor subjective sleep quality was associated with increased likelihood of hypertension. Similarly, in a review of 17 observational cohorts studies, which included a total sample of 58,924 participants with at least 1 year of follow-up data, Meng et al. found that insomnia was associated with an increased incidence of hypertension.

Although the link between insomnia and hypertension has gained wide acceptance, recent reviews note that this evidence is based upon clinic BP. However, clinic BP is markedly inferior to BP measured over 24-hours using wearable ABPM technology. In healthy adults, the normal circadian BP profile reveals that BP dips during the nighttime sleep period; importantly, a blunted nighttime BP dip (<10% dip in BP due to elevated nighttime BP) is the strongest BP predictor of CVD morbidity and mortality. Blunted nighttime BP dipping is characteristic of 30-40% of patients with hypertension, and there has been growing interest in strategies to target and lower nighttime BP in the management of hypertension. In patients with hypertension whose BP is managed using antihypertensive medications, there is compelling evidence that nighttime dosing of antihypertensive medications augments nighttime BP dipping. Moreover, this pharmacological chronotherapy has been shown to reduce the risk of adverse CVD events, underscoring that blunted nighttime BP dipping is an important mechanism contributing to

heightened CVD risk. However, for patients with insomnia and hypertension, it is possible that behavioral treatment of their insomnia may be a non-pharmacologic approach that could also benefit their BP as well as overall CVD risk. For example, current guidelines recommend consideration of non-pharmacologic interventions that include weight loss for overweight or obese patients, together with a heart-healthy diet comprising reduced sodium, lower saturated fat and limited alcohol consumption, which may lower systolic blood pressure (SBP) by approximately 11 mm Hg. Nonetheless, despite its association with hypertension and CVD risk, whether insomnia is a reversible CVD risk factor remains unknown.


10 years after completion of treatment. Sleep quality improvement following the CBT-I intervention may affect some mechanisms (e.g., augmented nighttime BP dipping) immediately, while other mechanisms (e.g., improved lipid profile) may emerge over several weeks, but could be sustained long term. Thus, our study design includes complete 6-month follow-up assessments in order to examine the possibility of progressive improvements in CVD risk mechanisms, and overall CVD risk.

In summary, the objective of this application is to further our understanding of the association between insomnia, hypertension, and CVD risk by focusing on the potential mechanisms involved. We aim to ascertain whether these mechanisms are affected favorably when sleep quality is improved by a behavioral intervention in those with insomnia, thereby also importantly determining whether poor sleep quality is a modifiable CVD risk factor. Exploratory aspects of this research study will include a focus on individual difference characteristics, with a particular interest in race, in view of extensive evidence that both poor sleep quality and nighttime BP non-dipping are especially common amongst African-American adults. Importantly, the study objectives are consistent with the call to consider nighttime BP a therapeutic target, and should help determine if interventions to improve sleep quality can favorably modify this characteristic of the circadian BP profile that appears to be a pathway leading to heightened CVD risk.

#### RESEARCH STRATEGY: B. INNOVATION

**Insomnia and CVD Risk Mechanisms** - To our knowledge, this is the first study that includes a sleep manipulation intervention as an approach to identifying the mechanisms that link insomnia to CVD risk. Several recent reviews and meta-analyses of this field have emphasized the need for studies designed to help identify these mechanisms. Previous studies have been limited by their cross-sectional designs, whereas the study proposed in this application should yield evidence of several mechanisms whereby insomnia conveys increased CVD risk.

The evidence that insomnia is a CVD risk factor has arisen from multiple observational studies, but whether it is a reversible risk factor is unknown - The proposed study will help establish whether those who respond to CBT-I with reduced insomnia symptoms and improved sleep quality are also likely to be characterized by ameliorated CVD risk.

Interventions that can achieve sustained improvements in sleep quality have the potential to abate the putative mechanisms that link insomnia to increased CVD risk – Because the improvement in sleep quality in response to CBT-I has been shown to persist for at least 10 years, the mechanisms conveying CVD risk are also likely to remain favorably modified. The proposed study includes a 6-month follow-up assessment to evaluate this possibility.

The mechanisms of insomnia-related CVD risk will be studied in the context of adults with hypertension – The proposed study will focus on adults with hypertension (and comorbid insomnia) because the presence of these two CVD risk factors has been shown to be interrelated, with their associated mechanisms of CVD risk also potentially shared. This patient population therefore affords the potential to show marked improvements in the mechanisms of CVD risk. The study outcomes should pave the

way for future research using CBT-I to target sleep in other medical conditions where insomnia is a common comorbidity.

## Design & Procedures

The study design reflects our objective of identifying the mechanisms responsible for the increased risk of CVD among patients with hypertension and insomnia, and to determine if these mechanisms can be favorably altered by improving sleep quality. We propose to utilize a behavioral intervention to manipulate sleep quality in 150 adults with hypertension and comorbid insomnia. This mechanistic clinical trial design will assign all 150 participants to a 6-week CBT-I intervention, which has been shown to markedly improve sleep quality and promote consolidated sleep in approximately 60% of those treated; whereas approximately 40% do not respond to CBT-I. While CBT-I is generally effective, the anticipated wide-ranging treatment response will provide the prerequisite variability in sleep quality changes that will afford us the opportunity to help identify the mechanisms by which insomnia conveys CVD risk and by which improved sleep may lower CVD risk. Our design (see Figure 5 below) will include a 6-week run-in period, without treatment, to document the stability of sleep quality, ABP, and CVD risk mechanisms, which will serve as a basis of comparison following CBT-I treatment. Assessments will be performed at baseline, after the 6-week run-in period, after the subsequent 6-week CBT-I intervention, and at 6-month follow-up. Importantly, the study design will also establish whether these insomnia-driven CVD risk mechanisms are modifiable by CBT-I for participants who show improved sleep following treatment.

**Screening Assessments.** Initial telephone screening will be used to ascertain whether potential participants are likely to meet the study eligibility criteria, with a focus on previously observed clinic BPs and the presence of insomnia symptoms. For those who are likely eligible, the first of two screening sessions will be scheduled, at which informed consent will be first obtained. A medical history will be taken for eligible participants. For women, menopausal status will be documented by self-reported menstrual bleeding, using the criteria described by Tom and colleagues. Status categories are postmenopausal (natural or surgical), perimenopausal, and premenopausal. Menopausal status will be considered as a potential covariate in analytic models.

**ReScreening** - If a participant fails to meet all eligibility criteria, but remains interested in participating in the study, they will have the option to be rescreened at a future date. If the rescreening occurs within 3 months, only the eligibility criterion which made them ineligible initially will be reassessed in order to ascertain their eligibility at rescreening; if rescreening occurs after more than 3 months, then the full screening protocol will be repeated. The participant will be re-consented at the time of rescreening.

**Office BP Screening Assessment.** At the first lab screening session, BP will be determined by unattended automated office blood pressure (AOBP) measurement using the Omron HEM-907 Professional Intellisense BP Monitor. AOBP measurement minimizes the “white coat” effect and correlates more closely with ambulatory BP than do standard office measurement techniques. After seating the individual in a quiet room, a cuff of appropriate size will be wrapped around the individual’s non-dominant upper-arm and the Omron HEM-907 will be operated in automated mode: After starting the

monitor, the Research Assistant will leave the room, and after a lapsed time of 5 minutes, the monitor will take a total of three BP measurements, each 2 minutes apart; the average of these three readings will be used to define office BP at that visit. If BP meets the studies inclusion/exclusion criteria, a second screening session will be scheduled, and if BP continues to meet criteria, the individual will be enrolled as a study participant (assuming all other inclusion/exclusion criteria are also met). This method for office BP assessment also will be completed subsequently at all four laboratory assessment sessions.

**Sleep Apnea Screening and Exclusion Assessments.** A previous diagnosis of obstructive sleep apnea (OSA) is an exclusion criterion. The Snoring, Tiredness, Observed apnea, high BP, BMI, Age, Neck circumference and male Gender (STOP-BANG) questionnaire will be used to screen potential study participants for OSA. Potential participants scoring  $>3$  on this scale, who otherwise meet all study eligibility criteria, will be required to complete a further screening assessment by the WatchPat device (Itamar Medical, Caesarea, Israel). The WatchPat device is a convenient tool that is worn in the comfort of potential participants' own bedroom and is found to be a sensitive and specific assessment for identifying the presence of OSA. Participants are given the option of using a Duke owned iPhone or their own smart phone that works with the WatchPat device. Potential participants showing an apnea-hypopnea index (AHI)  $> 15$  will be notified that they are no longer eligible to continue, and will be encouraged to seek additional evaluation and treatment through their physician. If someone has completed a polysomnography sleep test in the last 3 months, these results can be used instead of the Watchpat device.

### C.3. SLEEP MANIPULATION INTERVENTION

**Cognitive Behavior Therapy for Insomnia (CBT-I).** CBT-I is a well-established behavioral treatment for insomnia that successfully reduces insomnia symptoms and improves both subjective and objective measures of sleep quality. The approach to CBT-I for the proposed study is based on CBT-I programs that have been practiced and studied by research team members. CBT-I is manualized in a session-by-session guide. Our proposed study co-investigator, [name] serves as a consultant and trainer on the nationwide dissemination of CBT-I (see biosketch). [name] will train study therapists to deliver CBT-I in accordance with the training approach adopted by the CBT-I dissemination effort. Further, our sleep consultant, [name], will assist in the interventionist training and will oversee the fidelity measures and methods. CBT-I treatment will be delivered by [name] and one additional study therapist over 6 one-hour individual sessions.

**Intervention Training and Fidelity.** A second study therapist will be trained by [name], according to consensus guidelines. Initial didactic training (covering session-by-session procedures, core components of CBT-I) will last three days and be followed by training cases. The therapists will be allowed to provide the intervention once they have demonstrated 100% competence and adherence with all required treatment elements. The therapist will meet weekly for supervision throughout the trial. All therapy sessions will be recorded. A random selection of twenty percent will be rated for fidelity. In order to protect against drift, the frequency of fidelity checks will occur equally across the beginning, middle, and end of the intervention period. [name] will rate therapist treatment fidelity/adherence for recorded sessions using the adapted version of the Yale Adherence and Competence Scale. Recordings will be rated on the presence/absence of CBT-I elements. In addition, recordings will be rated on the

presence/absence of nonspecific treatment elements (e.g., therapeutic alliance, patient expectancies). Feedback from fidelity checks will be provided by Drs. [name] and [name].

**CBT-I Intervention Protocol Summary.** The CBT-I intervention will be delivered individually and in person by one of the therapists, over six one-hour weekly sessions. In circumstances where in-person visits prevent participation, the CBT-I intervention can be delivered via telephone. The CBT-I protocol is summarized below:

**Session 1: Sleep Education and Introductions to CBT-I and Sleep Diaries.** Participants will receive an overview of CBT-I treatment concepts and approach, in addition to education about sleep regulation processes and the cognitive and behavioral processes involved in the development of insomnia. At the end of the session, they will be instructed in establishing realistic treatment goals and the process for keeping weekly sleep diaries.

**Session 2: Introduction to Sleep Restriction Therapy and Stimulus Control.** The therapist will introduce Stimulus Control and Sleep Restriction Therapy guidelines and rationale. Sleep Restriction Therapy (SRT) is designed to strengthen the homeostatic sleep drive by restricting time in bed to actual sleep time as determined by sleep diary. The sleep “prescription”, or allowable sleep window, is gradually increased over the course of treatment to extend sleep duration. Stimulus Control is a set of instructions designed to strengthen the association between the bed/bedroom and sleep, and to establish a consistent sleep–wake schedule. Participants will receive education and intervention based on treatment targets identified in Session 1 in addition to the sleep pattern information gleaned from the sleep diary review. Sleep hygiene education will be provided for topics that are relevant to the participant (e.g., the effects of alcohol on sleep). An initial “sleep prescription” will be established and participants will be asked to follow this sleep schedule during the upcoming week. Cognitive therapy will be used, as needed, to address dysfunctional beliefs about sleep and to enhance adherence.

**Session 3: Introduction to Relaxation Therapy.** Participants will be introduced to Relaxation Therapy. The therapist will review the sleep diary with the participant and modify the sleep prescription, as needed, in accordance with SRT99 principles. Participants will be reinforced for adherence and progress. Barriers to adherence will be discussed and addressed using education, motivational enhancement, and cognitive therapy. Participants will be asked to practice relaxation strategies, follow their sleep prescription, and continue to track their sleep on diary during the upcoming week.

**Sessions 4 and 5: Sleep Prescription Titration.** The therapist will review the sleep diary with the participant and modify the sleep prescription, as needed, in accordance with SRT principles. Barriers to adherence will be discussed and addressed using education, motivational enhancement, and cognitive therapy. Participants will be asked to continue using relaxation strategies, follow their sleep prescription, and track their sleep on diary during the upcoming week.

**Session 6: Relapse Prevention.** The therapist will review the sleep diary with the participant and provide instruction on adjusting their sleep schedule after treatment, as needed. Treatment gains will be reviewed, and the therapist and participant will jointly develop a plan for ensuring that treatment gains are maintained.

#### C.4. ASSESSMENTS OF INSOMNIA AND SLEEP

The following laboratory-based and ambulatory assessments will be completed at baseline and repeated following the 6-week run-in control period, following the 6-week CBT-I intervention, and at 6-month follow up.

**Insomnia and Sleep Assessments.** Sleep will be assessed by both subjective and objective measures. Subjective measures will include sleep diaries, self-report measures of sleep quality, insomnia severity, and perceived daytime sleepiness. However, the primary measures of sleep quality and their anticipated changes following CBT-I will be actigraphy-based objective measures.

**Interview-Based Assessment of Sleep.** The Duke Structured Interview for Sleep Disorders (DSISD) follows DSM-V and the International Classification of Sleep Disorders criteria, and will be administered to identify those with insomnia disorder at screening. The DSISD was developed by the proposed study consultant, [name], and has been shown to have good reliability and validity.

**Actigraphy Sleep Assessments.** Sleep and daily physical activity will be recorded using an accelerometer (Actigraph GT9X Link, Actigraph, Pensacola, Florida), unobtrusively worn on the wrist of the non-dominant arm. The Actigraph GT9X monitor is a small, lightweight device that utilizes a 3-axis MEMS accelerometer, with motion sampled at a frequency of 30-100 Hz, and has been utilized and validated in both healthy and patient populations. Participants will wear the Actigraph 24 hours/day for 7 consecutive days, at baseline, upon completion of the 6-week run-in period, upon completion of the CBT-I intervention, and at 6-month followup. The actigraphy data will be processed using ActiLife and ActiLife+Sleep software (Actigraph, Pensacola, Florida), which was developed in collaboration with the US and international sleep and activity research community; scoring of actigraphy data will proceed in accordance with the guidelines of the Society of Behavioral Sleep Medicine. Recorded sleep log times, confirmed by an event marker, will be used to establish “lights out” and “out of bed” times. ActiLife+Sleep software will be used to derive our primary outcome measure of sleep quality, sleep efficiency (SE). Other sleep parameters of interest will be Time in Bed (TIB), total sleep time (TST), wake after sleep onset (WASO), and sleep fragmentation index (SFI). Sleep duration will be defined as TST (calculated by subtracting all periods of wakefulness from the time spent in bed). WASO is calculated by summing wakefulness periods after initial sleep onset and before final awakening. Sleep efficiency is defined as the ratio of total sleep time divided by TIB  $((TST/TIB)*100)$ . Sleep fragmentation is defined as the sum of percent mobile and percent immobile bouts less than 1-minute duration to the number of immobile bouts for a given interval. Actigraphy also provides reliable measurements of daily life physical activity and has been extensively validated against self-report, observational measures, and oxygen consumption estimates of physical activity. Therefore, the ActiLife software will also be utilized to derive daily cumulative step count and daily energy expenditure (kcal/d). All physical activity and sleep parameters derived using actigraphy will be based on the 8-consecutive-days monitoring protocol and represented as average daily activity/sleep values at each assessment phase (baseline, upon completion of the 6-week run-in period, upon completion of the CBT-I intervention, and at 6-month follow-up).

Subjective Assessments of Sleep. Subjective insomnia severity will be evaluated utilizing the Insomnia Severity Index (ISI). The ISI provides a global measure of perceived insomnia severity. Total scores range from 0-28, with higher scores indicating higher severity. The ISI has excellent internal consistency (Cronbach alpha = 0.74) and temporal stability ( $r = 0.80$ ). The ISI has been validated with sleep diaries and polysomnography (PSG). In clinical samples, a cut-off score of 11 was shown to have the greatest sensitivity and specificity for correctly identifying study participants meeting criteria for insomnia diagnosis. We also propose to use the Pittsburgh Sleep Quality Index (PSQI), a 19-item measure of sleep quality and disturbances over the past month, which has been shown to have internal consistency and validity. These subjective measures also will be used to document the extent to which the CBT-I intervention was effective at improving sleep quality in study participants, and are expected to show a strong association with changes in the objective actigraphy-based measures. Morningness Eveningness Questionnaire will assess circadian rhythms.

Daily Sleep Diaries. Subjective sleep estimates will be obtained concurrent with actigraphy. Participants will record their sleep using the recently developed consensus sleep diary to assure comparability across insomnia research studies. The sleep diary is considered the gold standard of self-reported sleep.

#### C.5. ASSESSMENT OF MECHANISMS OF CARDIOVASCULAR RISK

The following laboratory-based and ambulatory assessments will be completed at baseline and repeated following the 6-week run-in control period, following the 6-week CBT-I intervention, and at 6-month follow up. Assessors will be blinded to the study phase at which data are collected.

Office BP Assessment. Automated office BP (AOBP) will be obtained using the Omron HEM-907

Professional Intellisense BP Monitor. The office BP assessment protocol is described under “Office BP Screening Assessment” described earlier in this application.

24-hour Ambulatory Blood Pressure (ABP) Monitoring. We will use the Oscar 2 ABP monitor (Suntech Medical Inc., Raleigh, NC), which has been validated previously according to US and International standards. Study participants will be instrumented with the ABP monitor between 6:00-10:00 am on a typical weekday (Mon-Fri), and the monitor will be programmed to take BP measurements every 20 minutes throughout the waking hours and every 30 minutes during the nighttime sleep period. We have used this procedure with excellent participant acceptability and compliance in numerous previous studies. A successful 24-hour study will require at least 80% of the total readings to be valid, with no more than two consecutive hours lacking a valid reading, and at least one valid measurement per hour during the nighttime sleep period. Unsuccessful ABP studies will be repeated. Because a single 24-hour ABPM record has been shown to be of greater prognostic value than multiple clinic BP readings, it has become an accepted gold standard for evaluating intervention effects on BP. In addition to mean 24-hour ABP, mean waking and mean nighttime BP will be computed, with the nighttime sleep period defined by self-reported sleep logs, in accordance with the Society for Behavioral Sleep Medicine (SBSM) guidelines. Nighttime BP dipping will be defined as the percentage of the decline in nighttime SBP ( $((\text{mean daytime SBP} - \text{mean nighttime SBP}) / \text{mean daytime SBP}) \times 100$ ); SBP dipping defined in this way is a continuous variable that will be a primary outcome measure of sleep-related CVD risk mechanisms in

the proposed study. In addition, for descriptive purposes, a SBP dip  $\geq 10\%$  will be classified as normal “dipper”, while  $<10\%$  will be classified as “non-dipper”, with secondary analyses evaluating intervention effects on dipping status. As noted earlier in this application, the causes and consequences of blunted nighttime BP dipping has been a focus of our prior research. Importantly, our recent work shows that ABPM does not disturb sleep, and a single successful 24-hour ABP study provides adequate representation of the diurnal ABP profile in patients with hypertension. 24-hour ABP assessments will be obtained.

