**Analysis Plan:** General linear models will be used to examine the associations between improvements in sleep quality on improvements in BP dipping, controlling for age, gender, race, baseline sleep efficiency, baseline mean 24-hour BP, and pretreatment BP dipping, with post-treatment BP dipping as the criterion. Significance will a priori be set at  $P = .05$ . For follow-up analyses of 6-mo BP dipping, linear repeated measures mixed models will be examined in which 6-wk and 6-mo BP dipping both serve as outcome variables using the same covariates above. As an a priori explanatory analysis for our follow-up analyses, we will examine potential time X sleep efficiency interactions in order to examine the extent to which the association between sleep efficiency and BP dipping at six weeks differs from that at six-months. In addition, we will conduct an area under the curve analysis to examine overall associations that apply to both 6-wk and 6-mo in order to determine whether larger improvements in sleep are associated with larger improvements in BP outcomes in an overall sense. Because other ABP outcomes could plausibly be improved by CBT-I and also will reflect improved nighttime dipping, we will conduct parallel analyses of nighttime average BP and 24-hour BP levels.

**AIM 2:** Evaluate candidate mechanisms of CVD risk related to sleep quality in patients with hypertension and comorbid insomnia

**Hypothesis 2:** Improved sleep quality will be accompanied by: (i) reduced nighttime SNS activity; (ii) enhanced vascular endothelial function; (iii) reduced arterial stiffness, and; (iv) improved lipid profile.

**Analysis Plan:** General linear models will be used to examine the associations between improved sleep efficiency and improvements in mechanisms of CVD risk, controlling for age, gender, race, baseline sleep efficiency, and the pre-treatment (post run-in) level of the outcome. For our analyses of vascular endothelial function only, we also will adjust for baseline arterial diameter, consistent with our prior work. Follow-up analyses will follow the same approach as in Hypothesis 1, using linear repeated measures mixed models with 6-wk and 6-mo levels serving as the outcome variables.

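### Night SBP is averaged over the logged sleep period whatever the sleep state, so part of any link between sleep efficiency and dipping may reflect fewer awake readings rather than lower BP in sleep

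*Combined protocol and SAP*

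**What the plan says.** The Aim 1 outcome is nighttime SBP dipping, 100 x (day mean - night mean) / day mean. Of this measure C.5 (24-hour Ambulatory Blood Pressure Monitoring) says "SBP dipping defined in this way is a continuous variable that will be a primary outcome measure of sleep-related CVD risk mechanisms". On its inputs, the same paragraph says "mean waking and mean nighttime BP will be computed, with the nighttime sleep period defined by self-reported sleep logs" and cites a behavioral sleep medicine guideline. Readings are taken "every 20 minutes throughout the waking hours and every 30 minutes during the nighttime sleep period". Among the conditions for a valid record is "at least one valid measurement per hour during the nighttime sleep period". None of these conditions refers to sleep state.

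On the predictor, C.4 (Actigraphy Sleep Assessments) says "Sleep efficiency is defined as the ratio of total sleep time divided by TIB". For the limits of time in bed it says "Recorded sleep log times, confirmed by an event marker, will be used to establish" the lights-out and out-of-bed times. Actigraphy values are "represented as average daily activity/sleep values at each assessment phase", from 7 consecutive days of wear (the same paragraph later says 8). Each assessment has a single 24-hour BP record.

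The Analysis Plan for Aim 1 regresses dipping on improvement in sleep quality, "with post-treatment BP dipping as the criterion". It adjusts for age, gender, race, baseline SE, baseline 24-hour BP and pretreatment dipping. Nighttime mean BP and 24-hour BP get parallel analyses. No planned analysis is limited to readings taken asleep, and the text does not say that the ABPM day falls within the actigraphy week.

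**The concern.** In a sample with insomnia, some night readings will be taken while the participant lies awake. The night mean is then a mixture of asleep and awake-in-bed SBP, with weights of about SE and 1 - SE. The exposure is close to being an arithmetic weight inside the outcome. Adjusting for baseline SE and pretreatment dipping does not remove this, because the weight moves with the change in SE, which is the term being tested.

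The trial is explicitly mechanistic. Section D.2 says that it does not set out to establish the efficacy of CBT-I, and Section A.2 proposes that insomnia blunts the nocturnal fall in BP through sympathetic and vascular routes. A positive slope would naturally be read as support for that account. It could also arise, in part, with sleeping BP unchanged in every participant. The exploratory mediation analysis then uses the same dipping measure.

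**Working it through.** **The plan's own figures (Power and Sample Size Considerations).**
- Correlation: 150 x 0.85 gives about 127 analysed. By Fisher z, power for r = 0.25 is Phi(atanh(0.25) x sqrt(124) - 1.96) = Phi(0.88) = 0.81, which agrees with the stated 80%.
- Extreme thirds: 2 x ((1.96 + 1.04)/0.6)^2 = 50 per group, as stated. A 2.2-point difference at effect size 0.6 implies a dipping SD of 2.2/0.6 = 3.67 points.

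**Assumed inputs, not in the documents.** Waking SBP D = 135 mm Hg. Awake-in-bed SBP exceeds asleep SBP by G = 5, 10 or 15 mm Hg; the direction fits the Background's account of BP falling at night. The SD of SE change is 5 to 8 points.

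**Fixed window.** With asleep SBP A and SE as a fraction s, night SBP = sA + (1 - s)(A + G) = A + (1 - s)G. Holding A, G and D constant, the change in dipping = 100 x (change in s) x G/D. For a 10-point SE gain:
- G = 5: 10 x 5/135 = 0.37 points
- G = 10: 10 x 10/135 = 0.74 points
- G = 15: 10 x 15/135 = 1.11 points

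Induced correlation = (G/135) x SD/3.67. At G = 5 and SD 5 it is 0.05; at G = 10 and SD 5 it is 0.10; at G = 15 and SD 8 it is 0.24. The induced difference between extreme thirds is 2 x 1.0908 x SD x G/135, which runs from 0.4 to 1.9 points.

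**Several days of SE against one BP night.** If the multi-day mean tracks half of the BP night's SE (assumed), these ranges halve, to r of about 0.03 to 0.12 and 0.2 to 1.0 points.

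**Window shortened by treatment.** Session 2 of CBT-I (C.3) introduces sleep restriction, which shortens time in bed. Take the extreme case in which this produces the whole SE gain. Sleep stays at 6 h, time in bed falls from 8 h to 6/0.85 = 7.06 h (SE 75% to 85%), A = 115, and the 0.94 h moved into the day keeps its SBP of 115 + G. The waking mean becomes (16 x 135 + 0.94 x (115 + G))/16.94.

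| G | Night SBP | Waking SBP | Dip % | Change (points) |
|---|---|---|---|---|
| 5 | 116.25 to 115.75 | 135 to 134.17 | 13.89 to 13.73 | -0.16 |
| 10 | 117.50 to 116.50 | 135 to 134.44 | 12.96 to 13.35 | +0.38 |
| 15 | 118.75 to 117.25 | 135 to 134.72 | 12.04 to 12.97 | +0.93 |

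Changes are from unrounded values. At the smallest gap the sign reverses.

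**Chance of a significant slope.** This used waking SBP 140, SD of SE change 6, n = 127, a fixed window, and asleep SBP unrelated to SE. At G = 10, r = (10/140) x 6/3.67 = 0.12 and the chance of P < .05 is about 26%. At G = 15, r = 0.18 and the chance is about 50%. With half tracking these fall to about 10% and 16%. They are not false-positive rates for the total effect, because less time awake is part of that effect.

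**The case against.** The strongest reply is that less time awake is itself a way in which better sleep lowers night BP. Hypothesis 1 says only that improved sleep quality goes with more dipping and lower nighttime and 24-hour BP, so a measure over the whole logged night answers the question as posed. This stands. Dipping over the logged window is a legitimate total-effect outcome.

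The size is also open. The documents give neither the awake-asleep gap, nor the spread of SE change, nor the share of night readings taken awake. If the cited guideline bounds the night from diary sleep onset to final waking, time awake before sleep onset drops out and the weight is no longer exactly SE; wakefulness during the night would still count. The upper figures (r = 0.24, 1.9 points) need the largest gap and the largest SD together, with no attenuation and no shift in the window. These points stand too.

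Some protection is already planned. If time awake in bed is merely reclassified as daytime, the time-weighted 24-hour mean does not change, so the parallel 24-hour analysis helps to expose that case. WASO will also be explored. Neither isolates BP during sleep, and the nighttime-mean analysis contains the same awake readings as the primary outcome. The statement that ABPM does not disturb sleep does not address wakefulness caused by insomnia.

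A reader might go further and make any claim about the circadian profile conditional on the slope holding in asleep readings. The documents do not call for that. It would condition on post-treatment wakefulness, which is part of the effect studied, and let a noisier analysis overrule the primary one.

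**Conclusion.** The point holds as a limit on interpretation. The plan averages night SBP over a log-bounded window with no condition on sleep state, and SE is approximately the asleep share of a similarly bounded window. Part of an SE-dipping association may therefore reflect fewer awake readings, and no planned analysis separates that from lower BP during sleep.

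Under the stated assumptions the contribution for a 10-point SE gain is about 0.4 to 1.1 dipping points with a fixed window, and about -0.2 to +0.9 if the gain comes wholly from shorter time in bed. The yardstick is the plan's 2.2-point difference between extreme thirds. Tracking a single BP night with a multi-day SE mean reduces the contribution further.

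A reader might infer that any rise in SE must raise dipping, or that a positive result would be an artefact. The documents support neither: sign and size depend on figures they do not give, and the primary outcome remains valid as a total effect. Nor can it be said that the trial could never separate the two explanations. If the recordings overlap, asleep-only dipping could be computed; what is missing is the commitment to overlap and the pre-specification. This is a cheap improvement, not a fault that undermines the primary analysis.

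**What to change.** Keep dipping over the logged window as the primary outcome and add three things.

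1. In C.4 and C.5, state that the ABPM day falls within the 7-day actigraphy wear at each assessment.
2. In C.5, state that each night reading will be flagged asleep or awake from the actigraph epochs matching its time stamp.
3. In the Analysis Plan for Aim 1, pre-specify asleep-only SBP dipping, with the same model and covariates, as a supporting analysis, and report the share of night readings taken awake. Say that it serves to interpret the mechanism and is not a condition for the primary claim.

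If the slope persists in asleep readings, the case for a change in BP during sleep is stronger. If it shrinks, the report can say that the association partly reflects less time awake.

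The cost is some scheduling text, a time-stamp merge of the two recordings and one more model, with no added measurement for participants. The downside is fewer night readings per person, hence a noisier asleep mean, and some misclassification when actigraphy is used to label single readings.
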